6. INCLUSION AND EXCLUSION CRITERIA*

Patient Participants

Inclusion Criteria:

- Is eligible for LDCT for LCS follow-up
- Has technology to complete study activities (e.g., video call visit)
- English speaker

Aim 1 Additional Inclusion Criteria:

- Has UMMH PCP
- Has undergone LCS at UMMH in the past three years

Aim 2 Additional Inclusion Criteria:

- Has undergone LCS at UMMH
- Is overdue for LDCT follow-up

INVESTIGATOR STUDY PLAN - REQUIRED

Exclusion Criteria:

- Has previous diagnosis of lung cancer
- Has active cancer diagnosis
- Is a nursing home or group care resident
- Is pregnant

Stakeholder/Provider Participants

Inclusion Criteria Aim 1:

- Age ≥ 18
- Primary care provider/IT leader/lung cancer screening program leader/lung cancer screening navigator
- Works at UMass Memorial Health, Wake Forest Baptist Health, UCHealth, or UPenn

Inclusion Criteria Aim 2:

- Age ≥ 18
- Primary care provider
- Works at UMass Memorial Health

Vulnerable Populations

The following populations **will not be included** in this study:

- Individuals who are not yet adults (infants, children, teenagers)
- Pregnant women
- Adults unable to consent
- Prisoners

Since this is a small-scale study (~65 total subjects in 4 groups, with 3 different interviews and one intervention) it is not possible to have the study materials translated into other languages. If this pilot study shows promise, larger follow-up studies may focus on translating the intervention into additional languages.

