10. STUDY ENDPOINTS*

Primary outcomes are adherence to follow up LDCT and feasibility of Tele-Navi LCS. Adherence is defined as LDCT completion at 3, 6 and 12 months from the due date (as in previous studies; this definition may change depending on the status of COVID pandemic) and will be measured by EHR data.^{7,8,10-12} For feasibility, we will assess how engaged patients are during telehealth coaching, video-calls by tele-navigator, telehealth visit and patient portal use. We will assess intervention fidelity by recording and comparing all telehealth coaching and video-calls by a tele-navigator against a pre-defined checklist of key elements.

Secondary outcomes are occurrence of patient-provider communication after LDCT; communication modality used; contents of the communication assessed by EHR review and a patient survey; patient understanding of the result of LDCT and follow-up plan assessed by patient surveys; and perception and acceptability of the intervention from patient surveys and

INVESTIGATOR STUDY PLAN - REQUIRED

interviews and provider interviews. We will also measure cost by tracking time required for training for a Tele-Navigator, all the intervention components provided by the Tele-Navigator, and time and any other resources required to implement Tele-Navi LCS into clinical workflow.

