Medical record review will occur to assess annual LCS follow-up; record review may occur over several follow-up years (up to 4 years).

Figure 1. Aim 1 Study Activities

INVESTIGATOR STUDY PLAN - REQUIRED

If a patient mentions having difficulty with MyChart or with a clinical provider/office within our clinical system we will provide the patient with appropriate contact information to obtain assistance when feasible.

[figure not shown]
Aim 1 Stakeholder Participants: Additionally, brief demographic surveys and interviews will be conducted with LCS Stakeholders (e.g. PCPs, LCS navigators, LCS program leaders, Population-Health leaders and IT leaders) from UMMH, Wake Forest, UCHealth, and UPenn. All interviews will be audio recorded and transcribed. We will synthesize feedback from patient and clinical stakeholders and refine the workflow and intervention components of Tele-Navi LCS accordingly.

Aim 2 Patient Participants: We will recruit patients who meet study inclusion criteria. Participants will also be selectively enrolled (purposeful sampling) based on a variety of demographic and other criteria (e.g., by age, gender, smoking status, results of previous LDCT, years in the LCS program, MyChart use, technology device, characteristics of the primary care and ordering providers). Following recruitment, research staff will administer a baseline survey to participants. Study staff will also assist participants with obtaining access to the patient portal and coach them on how to use the portal and video-call (Telehealth Support). Educational materials will be sent to participants via mail/email (based on participant preference) prior to the educational outreach session.

Participants will receive a call (video call or telephone) from the Tele-Navigator to implement the rest of the intervention (Educational Outreach). Participants will be asked to complete a follow-up survey. We will also offer a truncated (5-item) version of the follow-up survey to participants who we have difficulty scheduling and completing the full version with; we will offer a reduced incentive (\$10) to complete this version. Finally, we will conduct medical record reviews to collect clinical outcomes data.

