22. SETTING

Patients will be recruited from primary care clinics at UMMH, as will stakeholders for Aim 2. Aim 1 stakeholders will be recruited from UMMH, Wake Forest, UCHealth, and UPenn. Research staff conducting recruitment, data entry, and analysis will complete study activities at the UMass Chan Medical School located in Worcester, MA.

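### LDCT adherence, a primary outcome, is taken from the EHR alone with no way to capture scans done outside UMMH, and the Aim 2 criteria omit the UMMH PCP requirement that the stated setting implies

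*Combined protocol and SAP*

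**What the plan says.** - **Outcome.** Section 10 names adherence as one of two primary outcomes: "Adherence is defined as LDCT completion at 3, 6 and 12 months from the due date". On its source it adds: "this definition may change depending on the status of COVID pandemic) and will be measured by EHR data".
- **Collection in Aim 2.** Section 11, under Aim 2 patient participants, agrees: "Finally, we will conduct medical record reviews to collect clinical outcomes data". Neither this section nor the analysis plan in Section 13 assigns patient report, outside-record requests or claims data to LDCT completion, or says how to code a scan done elsewhere.
- **Eligibility.** Section 6 lists a UMMH PCP among the additional Aim 1 criteria, directly above "Has undergone LCS at UMMH in the past three years". The additional Aim 2 criteria are past screening at UMMH, with no look-back limit, and "Is overdue for LDCT follow-up". There is no PCP line.
- **Setting.** Section 22 states: "Patients will be recruited from primary care clinics at UMMH, as will stakeholders for Aim 2". Section 4 also places the Aim 2 pilot in the screening workflow of those clinics.
- **Size.** Section 25 plans about 20 intervention patients. Section 13 states that no sample size calculation was made.

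**The concern.** A single-system record is an incomplete source for whether a scan took place. Where the record is silent, the patient may not have been scanned, or may have been scanned elsewhere. The plan does not separate the two, and an analyst with no rule is likely to read silence as no scan. Any such error lowers adherence and never raises it.

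The eligibility lists leave the gap wider than it need be. The PCP requirement, which would help keep follow-up inside the UMMH record, applies to Aim 1, where patients give a one-time interview. It is missing from Aim 2, where adherence is the outcome. On the written criteria, a patient screened at UMMH years ago and now followed elsewhere could enrol.

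No hypothesis test depends on this. What is at stake is the adherence estimate carried into the next study. Section 13 gives refinement of outcome measures as part of the pilot's purpose, so whether the EHR alone is an adequate source is something the pilot should find out.

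**Working it through.** The plan states no power, target or expected adherence for this pilot, so there is no figure to reproduce. The check has two parts.

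**1. Passages side by side**

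| Item | Aim 1 | Aim 2 |
|---|---|---|
| UMMH PCP in the criteria (Section 6) | yes | no |
| UMMH primary care setting (Sections 4, 22) | yes (Section 22) | yes (both) |
| Look-back on prior UMMH screening (Section 6) | three years | none |
| Named source for LDCT completion (Sections 10, 11) | record review | EHR data, record review |

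The Aim 2 criteria are therefore looser than the stated setting. Section 24 finds patients by searching the UMMH patient database, so the written criteria decide who is approached.

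**2. Size of the possible bias**

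Inputs:
- n = 20 (Section 25, approximate).
- True adherence p: 50% as a round example. For context, Section 5 cites 16-59% in community programs and more than 80% in comprehensive ones.
- q, the share of completed scans that are done outside and absent from the UMMH record: not in the documents, so assumed at 5% to 30%.
- Assumed coding: an absent record counts as not done.

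One missed scan costs 1/20 = 5 percentage points.

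Formula: observed adherence = p × (1 − q).

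- p = 50%, q = 10%: 0.50 × 0.90 = 45% (10 × 0.10 = 1 patient of 20 misclassified).
- p = 50%, q = 20%: 0.50 × 0.80 = 40% (10 × 0.20 = 2 patients of 20 misclassified).

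Across the adherence range cited in Section 5:

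| True p | q = 5% | q = 10% | q = 20% | q = 30% |
|---|---|---|---|---|
| 16% | 15.2% | 14.4% | 12.8% | 11.2% |
| 59% | 56.0% | 53.1% | 47.2% | 41.3% |
| 80% | 76.0% | 72.0% | 64.0% | 56.0% |

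The loss runs from 0.16 × 0.05 = 0.8 points to 0.80 × 0.30 = 24 points. For scale, the exact (Clopper-Pearson) 95% interval with n = 20 is 27% to 73% at 10/20 and 36% to 81% at 12/20.

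**The case against.** Several points can fairly be made for the plan.

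- **Chart review may hold outside reports.** Section 13 lists chart review as well as administrative EHR data, and a chart can contain outside results or notes. A reader might infer that every outside scan is scored as not done, but no section says so. This stands: the defect is a missing rule and a single source, and only scans that never reach the record are lost.
- **The setting already implies UMMH primary care.** Sections 4 and 22 point that way, and Section 24 describes the Aim 2 providers as UMMH providers of enrolled patients. This largely stands. Section 6 is silent for Aim 2 and does not contradict Section 22. Section 11 names "characteristics of the primary care and ordering providers" as a sampling characteristic, but that does not show that patients with outside PCPs will enrol.
- **Communication with providers.** It is tempting to extend the point to contact with outside providers. The documents do not support this: Section 10 has the "contents of the communication assessed by EHR review and a patient survey", and a survey can pick up outside contact.
- **Eligibility is confirmed before enrolment (Section 24).** This may catch a scan already done elsewhere. It cannot catch one done afterwards.
- **The survey may already ask.** Section 4 says that most Aim 2 materials come later, so the items cannot be seen. Even so, Section 10 gives the survey no role in measuring adherence.
- **Noise exceeds the bias.** With 20 patients, the interval is much wider than 5 to 10 points. That is true, but a one-directional error does not shrink in a larger study that uses the same measure.

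**Conclusion.** The point holds as a measurement gap in a primary outcome. EHR data are the only named source for LDCT completion, nothing is said about scans outside UMMH, and the Aim 2 criteria lack the PCP line that Aim 1 has and that the stated setting implies.

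The direction of any error is downward, at 5 points per missed scan with 20 patients. Its size is unknown. The fall from 50% to 45-40% assumes that 10-20% of completed scans are missed and that an absent record is coded as not done; neither assumption comes from the documents.

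A reader might also infer that patients overdue in UMMH records are especially likely to have moved their care. That is plausible, but the documents give no evidence for it and the conclusion does not rest on it. Because the pilot is descriptive, no error rate or decision threshold is affected.

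**What to change.** 1. **Section 6:** add the UMMH PCP requirement to the Aim 2 patient criteria so that they match Section 22, and apply it in the EHR search.
2. **Follow-up survey, full and 5-item versions:** add one item asking whether a screening chest CT was done elsewhere and, if so, when.
3. **Sections 10 and 13:** report adherence by EHR alone and by EHR plus self-report. Show outside or unknown scans as a separate category, not silently counted as not done.
4. **Labelling:** Section 9 expects participation to last about 3-6 months, so the survey may not cover the whole 12-month window. Label adherence after the survey date as EHR-only.

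The cost is one eligibility line, one search filter, one survey item and one coding rule. The recruitment pool becomes slightly smaller. Patients may over-report screening, which is why both versions are shown. The PCP requirement does not prevent outside scans, so the first change does not replace the second and third.

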11. PROCEDURES INVOLVED*

[figure not shown]
All recruitment and data collection materials will be submitted to the IRB for review and approval prior to use in the study. MyChart patient educational materials utilized by UMMH will also be utilized during the study (not research developed materials). All Electronic Health Record (EHR) and MyChart audit log data pulls will be requested following the UMass Chan [Research Informatics Core](#) processes (currently located here: <https://www.umassmed.edu/research-informatics/data-services/how-to-obtain-data/>). All interviews and study activities will be conducted at the convenience of the study participant and with safety precautions in mind; they will happen remotely (via phone, Zoom/Doximity, or similar). With explicit consent, interviews and study call activities will be audio-recorded and transcribed.

Aim 1 Patient Participants: We will recruit patients who underwent LCS within the past three years at UMMH. Potential subjects will be identified via the Electronic Health Record (EHR) (we may prioritize recruitment of eligible patients who have provided consent to re-contact from a prior study). Patients will be selected based on their age, gender, smoking status, adherence status, LDCT results (i.e., negative versus low-risk nodule), years in the LCS program, previous use of MyChart and telehealth, and access to necessary technology to use MyChart and telehealth. Following recruitment and screening, we will ask

patient participants to complete a baseline survey. Next we will ask participants to complete a one-time semi-structured interview to co-produce patient educational materials and the program to help patients complete follow-up LCS by using telehealth. Prior to the interview, the research team will select the focus of the interview and the questions based on the participant's previous MyChart and telehealth use, and the research team's needs to complete the development of Tele-Navi LCS. During this co-production, we will first explain current gaps in LCS adherence and the goals of Tele-Navi LCS. We will seek feedback on each element of the intervention: education materials and portal messages, as well as the overall concept of Tele-Navi LCS. Patient educational materials will be updated based on the input of participants; participant suggestions may be incorporated into subsequent interviews to seek additional feedback.

Medical record review will occur to assess annual LCS follow-up; record review may occur over several follow-up years (up to 4 years).

Figure 1. Aim 1 Study Activities

INVESTIGATOR STUDY PLAN - REQUIRED

If a patient mentions having difficulty with MyChart or with a clinical provider/office within our clinical system we will provide the patient with appropriate contact information to obtain assistance when feasible.

[figure not shown]
Aim 1 Stakeholder Participants: Additionally, brief demographic surveys and interviews will be conducted with LCS Stakeholders (e.g. PCPs, LCS navigators, LCS program leaders, Population-Health leaders and IT leaders) from UMMH, Wake Forest, UCHealth, and UPenn. All interviews will be audio recorded and transcribed. We will synthesize feedback from patient and clinical stakeholders and refine the workflow and intervention components of Tele-Navi LCS accordingly.

Aim 2 Patient Participants: We will recruit patients who meet study inclusion criteria. Participants will also be selectively enrolled (purposeful sampling) based on a variety of demographic and other criteria (e.g., by age, gender, smoking status, results of previous LDCT, years in the LCS program, MyChart use, technology device, characteristics of the primary care and ordering providers). Following recruitment, research staff will administer a baseline survey to participants. Study staff will also assist participants with obtaining access to the patient portal and coach them on how to use the portal and video-call (Telehealth Support). Educational materials will be sent to participants via mail/email (based on participant preference) prior to the educational outreach session.

Participants will receive a call (video call or telephone) from the Tele-Navigator to implement the rest of the intervention (Educational Outreach). Participants will be asked to complete a follow-up survey. We will also offer a truncated (5-item) version of the follow-up survey to participants who we have difficulty scheduling and completing the full version with; we will offer a reduced incentive (\$10) to complete this version. Finally, we will conduct medical record reviews to collect clinical outcomes data.

Pilot Testing: We will recruit (~ 12) Aim 1 patient participants to pilot test the intervention processes and data collection (telehealth support and educational outreach calls – we will conduct both in one call for the pilot testing). With participant feedback, we will make iterative edits to the intervention materials as they are pilot tested. We will submit final iterations to the IRB for review and approval prior to initiating the intervention. Pilot testing participants will not

Figure 2. Aim 2 Study Activities

INVESTIGATOR STUDY PLAN - REQUIRED

complete the Aim 2 surveys. We will offer a \$40 incentive to pilot test the intervention (one intervention call, ~40-60 minutes).

Aim 2 Provider/Patient Participants: Following completion of the intervention implementation, we will invite a sub-set of patient participants to complete an interview with study staff in order to obtain in-depth feedback. Separately, we will invite providers of patient participants to complete an in-depth interview.

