12. DATA AND SPECIMEN BANKING*

A limited data set will be securely stored for potential future use by the Principal Investigator. A limited dataset may be shared with study collaborators (with an executed Data Use Agreement) or with study funder/sponsors. A de-identified (by HIPAA standards) dataset may be made available to the public with PI approval; a data dictionary will be submitted to the IRB for review/approval prior to sharing the de-identified dataset.

13. Data Analysis and Management*

All patient-facing data collection materials will be submitted to the IRB for review and approval prior to use in the study. EHR and MyChart audit log data will be collected as described in the ISP, consent/fact sheet, HIPAA authorization/waiver materials reviewed and approved by the IRB.

Power analysis: The goal of this feasibility pilot is to determine the acceptability of the intervention and to estimate important process parameters (i.e. recruitment rates, completion rates of components) to inform a future study, including designing or refining outcome measures. As such, we have not conducted a sample size calculation.

Data analysis plan: To evaluate feasibility of Tele-Navi LCS, we will study process measures and effectiveness. Data sources include field notes, patient surveys, patient and provider interviews, Electronic Health Record (EHR) chart review, EHR administrative data and recording of telehealth coaching and a video-call. We will employ a mixed-methods process-outcomes pathway analysis.

Quantitative analysis: For measures of outcomes and intervention fidelity, we will present summary statistics with means and standard deviations of study variables. Further, we will create useful visualizations, including treatment cascades – a common graph used in quality improvement to identify gaps in the flow of patients to treatment (or follow-up screening and post-LDCT patient-provider communication in this case).

Qualitative analysis: We will analyze patient and provider interview transcripts to evaluate the acceptability of Tele-Navi LCS, understand their experiences, and elicit suggestions for improvement. Our analysis will be informed by constructs from the SCT, PRISM, and STM.

INVESTIGATOR STUDY PLAN - REQUIRED

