24. LOCAL RECRUITMENT METHODS

All recruitment materials will be submitted to the IRB for review and approval prior to use in the study. While we will not accept referrals for the study, for communication purposes with clinical providers we will share/post a study flyer with various clinical groups within UMass Memorial Health (from which we will be recruiting patients). This flyer is intended to provide clinicians notification that the study is active and to provide contact information in case clinicians have questions about the study; it will not be patient-facing.

Patients: We will use a variety of methods to identify and recruit a diverse group of patient participants. Working with the informatics group at UMMH/UMass Chan we will search the UMMH patient database to identify eligible patients. Eligible patients will be sent an invitation to participate. The invitation will make clear that participation is voluntary, and will include contact information for expressing interest, or declining participation. We will follow-up about one week later by telephone with invitees who do not respond. We will make up to 10 phone call attempts (over a period of two to three weeks, varying the time of day and day of week phone attempts are made) and leave no more than 3 total voicemail messages. Research staff will confirm eligibility prior to enrolling subjects. We have successfully recruited and completed comparable interviews and research activities with patients in previous studies utilizing similar recruitment methods.

Stakeholders/Providers: We will recruit stakeholders/providers to complete a one-time interview.

Aim 1: Potential stakeholder participants (for example PCPs, LCS navigators, LCS program leaders, and IT leaders from UMMH, Wake Forest, UCHealth, and UPenn) will be identified by the Principal Investigator, leadership at LCS programs, leadership within the Implementation Science Center for Cancer Control at Wake Forest UCHealth, and UPenn (which have already provided letters of support), and stakeholder participants in Aim 1 using snowball sampling.

Aim 2: Potential UMMH provider participants (providers of patient participants in the intervention group) will be recruited as study participants.

INVESTIGATOR STUDY PLAN - REQUIRED

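### Must the pilot name denominators for its recruitment and completion rates, given that its patients are purposefully selected?

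*Combined protocol and SAP*

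**What the plan says.** Under its power-analysis heading, Section 13 says the pilot is meant to judge acceptability and to "estimate important process parameters (i.e. recruitment rates, completion rates of components) to inform a future study"; it gives this as the reason for having no sample size calculation. The quantitative paragraph of that section reads: "For measures of outcomes and intervention fidelity, we will present summary statistics with means and standard deviations of study variables". The section also says that process measures will be studied, and it plans treatment cascades to show where patients drop out on the way to follow-up screening and to discussion of results. On sources it says: "Data sources include field notes, patient surveys, patient and provider interviews, Electronic Health Record (EHR) chart review, EHR administrative data", and it goes on to list recordings of the coaching and video calls.

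Section 10 describes feasibility in terms of engagement: "we will assess how engaged patients are during telehealth coaching, video-calls by tele-navigator, telehealth visit and patient portal use". It adds a fidelity checklist and, for costing, tracking of the Tele-Navigator's time on every component.

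Section 24 gives the recruitment sequence. A database search comes first, and then: "Eligible patients will be sent an invitation to participate". Non-responders are telephoned, up to 10 times. Finally: "Research staff will confirm eligibility prior to enrolling subjects". Section 11 supplies the selection sentence, "Participants will also be selectively enrolled (purposeful sampling) based on a variety of demographic and other criteria", and its examples include "MyChart use, technology device, characteristics of the primary care and ordering providers". Section 25 sets the intervention group at about 20 patients.

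On the components, Section 9 makes the telehealth support call depend on the participant finding it useful and requires one or more video calls with the navigator. Section 11 describes help with the portal and coaching without that condition, and allows the navigator's call to be by video or telephone.

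**The concern.** A recruitment rate has no meaning until its denominator is known. Section 24 offers at least four: listed as eligible in the database, invited, reached, and confirmed eligible. They need not be close. Access to suitable technology is an inclusion criterion in Section 6, and nothing says the database records it, so some invited patients may prove ineligible on the telephone. If staff also choose among willing patients, enrolled over reached partly measures staff choice and understates willingness.

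Completion is open in a similar way. An optional support call can be counted out of everyone enrolled or out of those who wanted it. A patient contacted only by telephone has completed outreach on Section 11's wording but not on Section 9's. In addition, two of the selection factors, portal use and device, are ones that could plausibly influence uptake of a telehealth component.

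What is at stake is planning of the next study. A rate carried forward with the wrong denominator would misjudge how many patients to invite.

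**Working it through.** The plan states no rate, precision or sample size figure, so there is nothing to reproduce. The only input from the documents is n of about 20 (Section 25); every other count below is assumed for illustration.

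**1. Recruitment denominator.** Let c be the share of invited patients who are reached and f the share of those reached who prove ineligible. Then

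[enrolled/(reached and eligible)] ÷ [enrolled/invited] = 1/(c(1 − f)).

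With 100 invited, 70 reached and 14 of those ineligible:
- per invited: 20/100 = 20.0%
- per reached: 20/70 = 28.6%
- per reached and eligible: 20/(70 − 14) = 20/56 = 35.7%

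Over c from 0.5 to 0.8 and f from 0.1 to 0.3, the ratio runs from 1/(0.8 × 0.9) = 1.39 to 1/(0.5 × 0.7) = 2.86. Against 20.0% of invited, that is 27.8% to 57.1%. This range is an identity evaluated at chosen inputs; the documents do not say what c and f are.

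**2. Timing of selection.** If 100 are reached, 40 are willing and staff then choose 20, enrolled/reached is 20/100 = 20% while willingness is 40/100 = 40%. If selection comes before invitation, this gap does not arise. Timing bears mainly on recruitment: completion rates describe the selected patients whenever the selection was made and whatever denominator is used.

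**3. Support call.** If k of 20 want it and all but one of those complete it:

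| k | Out of all enrolled | Out of those wanting it |
|---|---|---|
| 5 | 4/20 = 20% | 4/5 = 80% |
| 10 | 9/20 = 45% | 9/10 = 90% |
| 20 | 19/20 = 95% | 19/20 = 95% |

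**4. Outreach mode.** If 18 of 20 are contacted, 2 to 6 of them by telephone only, completion is 18/20 = 90% on Section 11's wording, and 16/20 = 80% to 12/20 = 60% on Section 9's.

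**5. Selected mix.** With s the share of prior portal users, crude completion = s × p(user) + (1 − s) × p(non-user). At 90% and 50%, moving s from 0.2 to 0.5 to 0.8 gives 58%, 70% and 82%. At 90% and 70% it gives 74%, 80% and 86%. If completion does not depend on portal use, the mix has no effect. For comparison, 14/20 = 70% has an exact 95% interval of 45.7% to 88.1%, and 16/20 = 80% has 56.3% to 94.3%. Each interval covers the shifts around it, so 20 patients could not separate a mix effect of this size from chance.

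**6. What the procedures already record.** Staff cannot keep to a limit of 10 calls and 3 voicemails per patient (Section 24) without a contact record for each invitee. Eligibility is confirmed individually. Section 30 requires verbal consent to be documented with its date. Component delivery can be read from call recordings, the Tele-Navigator's tracked time and the portal audit logs (Sections 10, 11 and 13).

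In steps 1 to 4, each pair of competing rates comes from one set of counts. Once the counts are shown, the ambiguity is gone.

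**The case for a change.** The best case for a change is that the plan rests its lack of a sample size on estimating exactly these rates, and then defines neither. Section 10 leaves recruitment out of feasibility, the cascades are described only for screening and communication and name no starting population, and a screening log appears only as an item in the generic upload checklist. Counts of patients never reached, found ineligible, or willing but not chosen are hard to rebuild later, whereas a few sentences now would cost almost nothing.

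Much of this stands. No denominator is named, the selection step is not placed in the sequence, and Sections 9 and 11 do not agree on call mode or on the condition for support. The willing-but-not-selected count is the weakest spot, since it relies on staff noting the reason for non-enrolment.

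It does not follow that the plan gives a wrong result. No stated formula or number is in error, and no test, interval or go/no-go threshold depends on these rates. Completion data are clearly going to be collected; only the way of expressing them is unstated. Misuse in planning would require someone to apply a per-eligible rate to invitations, which a report giving the counts prevents. A split of about 20 patients by prior portal use would be a reporting preference with very little information in it.

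**Conclusion.** No change to the plan follows. The missing denominators and the unplaced selection step are details that the analyst of a descriptive, single-group pilot would ordinarily supply by reporting patient flow from invitation to enrolment, uptake out of all enrolled, and video and telephone contacts separately. The difference between Sections 9 and 11 is a looseness of wording that such a report handles. Purposeful sampling is a fair trade-off here: it gains a varied group for feedback and gives up representativeness that about 20 patients could not provide in any case.

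If bare percentages were reported, the recruitment rate could differ by a factor of about 1.4 to 2.9 on the assumed contact and ineligibility rates. With counts shown, nothing is lost. The documents do not show the size of any effect of selection on completion.

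This rests on staff keeping the contact record that Section 24 implies and on the report giving counts. It is also limited to the visible text: Figure 2 is not reproduced, and Section 4 defers most Aim 2 materials to a later submission, so definitions may exist there.
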